## **Exposure (vaccination)**

#### Exposure of interest

The exposure of interest is vaccination with any influenza vaccine (seasonal or pandemic) in the season under investigation. It is crucial to know precisely the date of vaccine administration, the type/brand of the vaccine and the date of symptoms' onset as well as the date of specimen collection.

The vaccine type specific VE may be assessed e.g.

- by strategy used for influenza antigen preparation (live attenuated, inactivated, subunit, split virion),
- by number of vaccine virus strains contained in the different vaccines available (trivalent, tetravalent)
- by adjuvant (adjuvanted, non-adjuvanted)
- by vaccine dose (one dose, two doses; 0,25 ml, 0,5 ml)
- by manufacturing process (egg-based, cell-based)

The vaccine types selected to primary and potential sensitivity analyses will be specified in the generic study site level SAP, which will be updated annually, if needed.

#### Vaccination status ascertainment

The sources of information for the vaccination status may include:

- vaccination registry
- consultation of the patient's vaccination card
- interview with the patient's GP
- interview with the patient's pharmacist
- data from the patient's insurance company showing evidence of pharmacy delivery or reimbursement of influenza vaccine during the current influenza season

An interview of the patient and/or their relatives alone is not a preferred method of vaccine status ascertainment but may be performed. When vaccination status is positive according to any of the above sources but not recalled by patient, they will be coded as vaccinated. When positive vaccination status is indicated only by recall or is otherwise ambiguous, the vaccination status will be coded as "potentially vaccinated".

> Each study site to describe the precise way of vaccination status ascertainment.

#### Definition of vaccination status

An individual aged  $\geq$ 9 years, or a child aged <9 who has been fully vaccinated (at least two injectable doses or one LAIV dose) during the previous influenza season will be considered as

- vaccinated with the influenza vaccine of interest if he/she has a record of influenza vaccine administration >14 days before ILI/SARI symptom onset (see section Vaccination status ascertainment)
- partially vaccinated if he/she has a record of influenza vaccine administration ≤14 days

before ILI/SARI symptom onset

- **unvaccinated** if he/she has no influenza vaccine record for the current season
- **potentially vaccinated** if the positive vaccination status is based on recall alone and cannot be confirmed by registers, or is otherwise ambiguous.

A child aged < 9 years who has not been fully vaccinated (see above) during the previous influenza season will be considered as

- **vaccinated** with the influenza vaccine of interest if >14 days have elapsed since the second record of injectable vaccination or the first record of LAIV vaccination during the current season (see section *Vaccination status ascertainment*)
- partially vaccinated
  - during the first 14 days after the second record of injectable vaccination or the first record of LAIV vaccination during the current season
  - after the first record of injectable vaccination until >14 days have elapsed since the second record of vaccination during the current season
- **unvaccinated** until the first vaccination record during the season
- **potentially vaccinated** if the positive vaccination status is based on recall alone and cannot be confirmed by registers, or is otherwise ambiguous.

The *partially* and *potentially* vaccinated groups will be excluded from primary analysis; their significance will be assessed in sensitivity analyses.

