# Annex 1: Minimum dataset requirement

## DRIVE – Minimum dataset for pooled data analysis (case-control studies) v4 16 Oct 2018

Variable	Obligatory	Description	Additional info	Format	Values/coding	Example
		Country code				
		defined in ISO				
idcountry	Obligatory	3166-1 alpha-2		2 letters text		UK
idstudy	Obligatory	Name of the study		Text		JorviTND
region	Optional	Region name		Text		Wales
	Obligatory					
	(for studies	Identifier of the				
	which	GP practice or				
	include >1	hospital where				
	GP offices /	the patient was				
idunit	hospitals)	seen		Text		JS123
		Type of unit				
		(outpatient, e.g.			1=Outpatient	
		GP practice, or			2=Inpatient	
		inpatient, e.g.		Numeric	9999=No	
setting	Optional	hospital)		(Categorical)	information	2
		Patient				
		identification		Unique		
id	Obligatory	number		integer		101
				Numeric	0=Female	
sex	Obligatory	Sex		(Binary)	1=Male	0
		Age in years (at				
		the onset of the				
age	Obligatory	symptoms)		Numeric		1984

DRIVE ///363	– D7.1					
		Age in months				
	Obligatory	(only for children				
	for children	<1 years old. Else				
	<1 year of	should not be				
agemonths	age	provided.)		Numeric		6
		Date of symptoms			Date within the	
onsetdate	Obligatory	onset		dd/mm/yyyy	study period	29/12/2017
					Date within the	
swabdate	Obligatory	Date of swabbing		dd/mm/vvvv	study period	30/12/2017
		Date of visit to the				
		GP or admission	In hospital, the first point of contact		Date within the	
visitdate	Obligatory	to the hospital	(often, arrival at the emergency room)	dd/mm/yyyy	study period	30/12/2017
		Has the nationt	During bosnitalization or within 20 days	Numoric	0-1100	
doath	Ontional	diod2	after discharge	(Pipany)	1-Dood	0
ueath	Optional	uleu!		(Billary)	I-Deau	0
					Date within the	
deathdate	Optional	Date of death		dd/mm/yyyy	study period	99/99/9999
					0=No	
			A measured fever of ≥38°C or		1=Yes	
		Fever or	temperature 37-38°C with patient-	Numeric	9999=No	
fever	Optional	feverishness	reported feverishness	(Categorical)	information	1
					0=No	
					1=Yes	
				Numeric	9999=No	
headache	Optional	Headache		(Categorical)	information	1
					0=No	
					1=Yes	
				Numeric	9999=No	
myalgia	Optional	Myalgia		(Categorical)	information	0

					0=No	
					1=Yes	
				Numeric	9999=No	
malaise	Optional	Fatigue/Malaise		(Categorical	information	1
					0=No	
					1=Yes	
		Sudden onset of		Numeric	9999=No	
suddenonset	Optional	symptoms	Within 7 days before admission	(Categorical)	information	1
					0=No	

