		influenza		1=Yes	
		vaccination in	Numeric	9999=No	
seasvaccany	Obligatory	current season	(Categorical)	information	1
					Vaxigrip
seasvaccbrand	Obligatory	Vaccine brand	Text		tetra
		Date of influenza			
		vaccination in			
seasvaccdate	Obligatory	2017-2018	dd/mm/yyyy		11.1.2018
		Received			
		influenza		0=No	
		vaccination in		1=Yes	
		previous season	Numeric	9999=No	
seasvaccn1	Optional	(season n – 1)	(Categorical)	information	
		Dessived		0.14-	
		Received			
			Numerie	1=Yes	
	Ontional		Numeric	9999=NO	
seasvacchz	Optional	season n – z	 (Categorical)	Information	
		D is the strict $l < 0$			
		Did the kid (< 9		1=Yes	
		years) receive 1st		999=NOt	
		dose of influenza	Numorio		
coord coold d	Obligatory	Vaccination in		9999=NO	000
SEASVALLKIUI	Obligatory		(Categorical)		999
		Did the kid (<0			
		Did the kid (<9		1-165 000-Not	
		doso of influenzo		299=NUL	
		uose or influenza	Numoria		
	Obligator			9999=NO	000
seasvacckid2	Ubligatory	current season?	(Categorical)	information	999

	Only if					
	Seasvacckid1					Vaxigrip
seasvaccbrand1	is 1	Vaccine brand		Text		tetra
	Only if					
	Seasvacckid2					Vaxigrip
seasvaccbrand2	is 1	Vaccine brand		Text		tetra
		Date of 1st dose				
		of influenza				
		vaccination in the				
	Only if	current season				
	Seasvacckid1	(only if			≥Date within the	
seasvaccdate1	is 1	Seasvacckid1=1)		dd/mm/yyyy	study period	11.1.2018
		Date of 2nd dose				
		of influenza				
		vaccination in the				
	Only if	current season				
	, Seasvacckid2	(only if			≥Date within the	
seasvaccdate2	is 1	Seasvacckid2=2)		dd/mm/yyyy	study period	11.1.2018
					0=No	
		Received any			1=Yes	
		pneumococcal		Numeric	9999=No	
pneumovac	Optional	vaccination	Any time.	(Categorical)	information	1
		Date of	· ·			
		pneumococcal				
pneumovaccdat	Optional	vaccination	Latest dose.	dd/mm/vvvv		11.1.2018
					0=No	
		Does the patient			1=Yes	
		have at least one	Including obesity (BMI ≥30). Not	Numeric	9999=No	
chronic	Obligatory	chronic disease?	including smoking or pregnancy.	(Binary)	information	1

DRIVE 777363 – [	07.1		imi	innovative medicines initiative		
			Any of the following dg codes (ICD-10):			
			В18, К70-74, К75.0-75.1, К75.3-75.9,			
			К76-			
			77 INCLUDING:			
			Alcoholic liver disease, Toxic liver			
			disease, Hepatic failure, Chronic			
			hepatitis (viral & other), Fibrosis and			
			cirrhosis of liver, Other inflammatory			
			liver diseases, Other diseases of liver		0=No	
			EXCLUDING: Clinically insignificant liver		1=Yes	

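### For some children under 9, primary-analysis vaccination status depends on last season's dose count or LAIV use, which the Annex 1 minimum dataset does not collect

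*Combined protocol and SAP*

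**What the plan says.** The protocol (Methods, Definition of vaccination status) has two exposure rules. The first covers everyone aged 9 or over and also "a child aged <9 who has been fully vaccinated (at least two injectable doses or one LAIV dose) during the previous influenza season". Under it, one vaccination record more than 14 days before symptom onset makes the person vaccinated. The second covers all other children under 9. They count as vaccinated only "if >14 days have elapsed since the second record of injectable vaccination or the first record of LAIV vaccination during the current season"; until then a child with a dose on record is partially vaccinated.

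The label decides who is analysed: the partially and potentially "vaccinated groups will be excluded from primary analysis; their significance will be assessed in sensitivity analyses".

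Annex 1 sets out the minimum dataset for the pooled case-control analysis. Its vaccination items are:

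- **Current season, children under 9:** whether a first and a second dose were given (`seasvacckid1`, `seasvacckid2`), with brand and date for each.
- **Last season:** `seasvaccn1`, labelled optional and coded no, yes or no information. It holds no number of doses, brand or LAIV indicator.

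The section Potential confounders and effect modifiers marks influenza vaccination in at least one previous season with an asterisk, meaning it belongs to the minimum set for pooling. It does not ask for doses or vaccine type either.

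**The concern.** The fact that selects the rule for a child under 9 is not among the data that sites must supply. The child whom the first rule was extended to cover, fully vaccinated last season and given one injectable dose this season, cannot be told apart from a child who had a single injectable dose last season. The first belongs in the exposed group and the second is to be left out of the primary analysis.

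What is at stake is the make-up of the vaccinated group among young children, and so the age-specific objective for 6 months to 14 years and the objective on previous vaccination. The unvaccinated reference group is not touched, because a child with no current-season record is unvaccinated under both rules.

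**Working it through.** The plan states no figure on this point, so there is none to reproduce. The check applies both rules to the possible current-season patterns and then asks what Annex 1 can resolve.

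**Step 1. Apply both rules to eight current-season patterns of a child under 9.** Days are counted back from symptom onset. Courses mixing LAIV and injectable vaccine are left out.

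| Current season | Fully vaccinated last season | Not fully vaccinated last season | Depends on history? |
|---|---|---|---|
| No dose | unvaccinated | unvaccinated | no |
| One injectable, ≤14 days | partial | partial | no |
| One injectable, >14 days | vaccinated | partial | **yes** |
| Two injectables, both >14 days | vaccinated | vaccinated | no |
| Two injectables, first >14, second ≤14 days | vaccinated | partial | **yes** |
| Two injectables, both ≤14 days | partial | partial | no |
| One LAIV, >14 days | vaccinated | vaccinated | no |
| One LAIV, ≤14 days | partial | partial | no |

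Last season matters in 2 of 8 patterns. For the fifth row I let the first dose satisfy the first rule, although the later dose also fits that rule's wording for partial vaccination.

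**Step 2. Map last season's history to `seasvaccn1`.**

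| History last season | Fully vaccinated? | `seasvaccn1` |
|---|---|---|
| No dose | no | 0 |
| One injectable | no | 1 |
| Two injectables | yes | 1 |
| One LAIV | yes | 1 |
| Unknown or not supplied | undetermined | 9999 or blank |

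Only the value 0 settles the status. The value 1 mixes one history that is not full with two that are, so no child can be confirmed as fully vaccinated from this item.

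**Step 3. Size.** The documents give neither the share of participants under 9 nor the distribution of doses, so the number affected cannot be calculated. The cost in precision if unresolved children are excluded can only be illustrated. *Assumptions, none from the documents as a description of these children:* 200 child cases and 200 controls, 20% coverage, true VE 50%.

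- With OR = 0.5, the Annex 3 cell formulas give a = 29.14, b = 50.86, c = 170.86 and d = 149.14.
- Formula (3) gives 1 − 0.5 × exp(1.96 × √(1/29.14 + 1/50.86 + 1/170.86 + 1/149.14)) = 1 − 0.5 × exp(1.96 × 0.258) = 17.1%.
- Removing a share s of the vaccinated, with the unvaccinated cells fixed, divides (1/a + 1/b) by (1 − s). For s = 20%, 40% and 60% the lower limit becomes 12.9%, 6.3% and −6.1%.

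The value of s is a free choice. In the 6 months to 14 years stratum it is held down by children aged 9 to 14 and by children in the unaffected patterns.

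**The case against.** The best defence has two parts.

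First, Annex 1 is a minimum and not a ceiling. Annex 4 pools site estimates in two stages, so a site can apply the rule itself before pooling. Sites must describe how they ascertain vaccination, and Sources of information lets them use registers, vaccination cards and GP interviews for previous status. This stands as far as it goes: a site with a register can classify these children correctly. But nothing in the documents tells a site to record last season's doses or to submit a derived status, so handling may differ between sites, against the Preface's aim of maximum harmonisation.

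Second, the plan has somewhere to put unresolved cases. Positive status that is otherwise ambiguous is coded potentially vaccinated, and Missing data excludes subjects with missing exposure. Unknown dose history is not named in either place, but it is reasonable to send it there. This also stands. A reader might infer that analysts are forced to treat every previous vaccination as full or none as full; the ambiguous category means they are not. What remains is that exclusion falls selectively on children who were, or may have been, vaccinated last season, and some of them meet the plan's own definition of vaccinated.

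**Conclusion.** The gap is real but narrow. The part of the first rule that covers children under 9 cannot be carried out from the pooled minimum dataset in the two affected patterns unless `seasvaccn1` is 0. The result is either a selective loss of repeat vaccinees from the exposed group, or site-to-site differences with a risk of counting partially vaccinated children as vaccinated. This rests on the vaccination rows of Annex 1, which read consecutively although other parts of the table are broken.

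Three stronger readings are not supported:

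- **That children under 9 as a group cannot be classified.** Six of the eight patterns have the same status whatever happened last season.
- **That VE is biased by a stated amount.** The documents give neither the one-dose VE nor the share of children affected. The precision figures above are illustrations only.
- **That neighbouring oddities in Annex 1 add to the fault.** The range shown for child dose dates might suggest that doses given before virus circulation would be rejected, but the Study period section lets the joint period be extended to cover the vaccination campaign. The condition "Seasvacckid2=2" is clerical, because the same row's obligation column requires the value 1.

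**What to change.** 1. In Annex 1, make one of the following obligatory for children under 9: (a) last season's number of doses (0, 1, 2 or more, unknown) and whether any was LAIV; or (b) a flag derived by the site for fully vaccinated last season (yes, no, unknown).
2. State that unknown history in the two affected patterns is coded potentially vaccinated, so that these children leave the primary analysis and enter the sensitivity analysis in the same way at every site.
3. Reconcile the optional label of `seasvaccn1` with the asterisk on previous-season vaccination in Potential confounders and effect modifiers.

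The dose rule itself is not changed. The cost is one or two extra codebook fields for young children. Sites without access to last season's records will enter unknown, but the resulting exclusions will then be uniform and can be counted.

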## **Study period**

The seasonal assessment will start when the influenza virus circulation begins (first virus detected at the national/study site level) in the country/region and will finish at the end of the influenza season (no cases detected during 2 consecutive weeks or equivalent).

Each study site to specify the assessment period: the definition of the beginning, peak and end of the influenza period at the study site according to the information provided by the local influenza surveillance system (including information on the type of virus circulating and virulence of the virus)

For the joint analysis, a harmonised minimum period will be defined (e.g. from week 40 till week 20), but if needed, it will be extended to fully cover the vaccination campaign and the epidemic in each study site. Definition of shorter time periods (e.g. early, middle and end season) will be developed to take into account differences in influenza activity over time and probable development of immunity in unvaccinated population through encounters with the circulating viruses

For addressing the secondary objective of estimating influenza vaccine effectiveness over several seasons, multiple study periods will be combined.

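### For most subjects the unvaccinated category looks at the whole season rather than at symptom onset, so anyone first vaccinated after onset has no category and leaves the comparator

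*Combined protocol and SAP*

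**What the plan says.** The section Definition of vaccination status (protocol, Methods, Exposure) has two blocks.

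- **First block:** subjects aged 9 or over, and children under 9 who were fully vaccinated in the previous season. Vaccinated means the subject "has a record of influenza vaccine administration >14 days before ILI/SARI symptom onset". Partially vaccinated means the subject "has a record of influenza vaccine administration ≤14 days" before onset. Unvaccinated applies "if he/she has no influenza vaccine record for the current season", with no reference to onset.
- **Second block:** the other children under 9. They count as unvaccinated "until the first vaccination record during the season".

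In both blocks, potentially vaccinated applies "if the positive vaccination status is based on recall alone and cannot be confirmed by registers, or is otherwise ambiguous". Of this category and the partial one, the section says that such "vaccinated groups will be excluded from primary analysis; their significance will be assessed in sensitivity analyses". No rule is given for a dose dated after onset.

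Three other places bear on the point. Study period says of the harmonised minimum period that, if needed, "it will be extended to fully cover the vaccination campaign and the epidemic in each study site". Vaccination status ascertainment accepts insurer evidence of delivery or "reimbursement of influenza vaccine during the current influenza season", with no cut-off at onset. In the Annex 1 codebook, seasvaccany asks about vaccination in the current season and is not tied to onset; the date is held separately in seasvaccdate.

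**The concern.** In a test-negative study, exposure has to be the subject's status when the illness began. In the first block, two categories look back from onset and the third looks at the whole season, including the part after onset. Someone unvaccinated when they fell ill and vaccinated some weeks later was a valid unvaccinated case or control at onset, but the wording removes them.

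Who gets removed depends on later behaviour and on calendar time. Most such subjects fall ill while the campaign is still running. If the test result also affects whether a person is vaccinated afterwards, cases and controls are removed at different rates within the same week and the odds ratio shifts.

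Annex 3 uses one unvaccinated group for every brand-specific estimate, so any distortion is shared across the primary objective. Sites may also resolve the gap differently: drop the subject, code the negative interval as partially vaccinated, keep the subject as unvaccinated, or apply the ascertainment rule that a positive source overrides lack of recall and code the subject as vaccinated. That would add avoidable differences between the site estimates that are later pooled.

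**Working it through.** **1. Does any category fit?** Take a first-block subject whose only dose is dated 20 days after onset.

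| Category | Requirement | Met? |
|---|---|---|
| Vaccinated | record more than 14 days before onset | no |
| Partially vaccinated | record 14 days or fewer before onset | no, the dose is not before onset |
| Unvaccinated | no record in the season | no, a record exists |
| Potentially vaccinated | recall only, or ambiguous | no, the record is dated |

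Under the second-block rule the same subject would be unvaccinated at onset.

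**2. Effect on the odds ratio.** Let a and b be vaccinated cases and controls, and c and d unvaccinated cases and controls, so OR = ad/(bc). Dropping a fraction q1 of c and q0 of d gives

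OR′ = OR × (1 − q0)/(1 − q1), and VE′ = 1 − OR′.

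**3. Reference scenario.** Sample size considerations states that 500 cases at 1:1 with a true VE of 50% give a lower 95% limit above 30% for coverage above 20%. Annex 3, equation (3), at 20% coverage has a = 72.8, b = 127.2, c = 427.2, d = 372.8. Then 1 − 0.5 × exp[1.96 × √(1/72.8 + 1/127.2 + 1/427.2 + 1/372.8)] = 31.2%. At 50% coverage the limit is 35.7%. The plan's figure is reproduced and is not in dispute.

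**4. The same scenario with losses (20% coverage).** The q values are assumptions; the documents give none.

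| q0 (controls) | q1 (cases) | VE′ | Lower limit |
|---|---|---|---|
| 0 | 0 | 50.0% | 31.2% |
| 10% | 10% | 50.0% | 30.9% |
| 10% | 5% | 1 − 0.5 × 0.90/0.95 = 52.6% | 34.6% |
| 5% | 10% | 1 − 0.5 × 0.95/0.90 = 47.2% | 27.2% |
| 20% | 5% | 1 − 0.5 × 0.80/0.95 = 57.9% | 41.8% |

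Equal loss costs a little precision and causes no bias. Unequal loss moves VE in either direction.

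**5. Over a season, stratified by onset week.** Large q0 values arise only early in the campaign, when cases are usually few, so the last row cannot be read as a season estimate. Assume a 30-week season from week 40, final coverage 50%, a campaign centred 5 weeks in (SD 2 to 3 weeks), epidemic peaks at 10, 14 or 18 weeks (SD 2.5 to 3.5 weeks) and a true VE of 50%. Week-stratified (Mantel-Haenszel) VE under the written rule:

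| Assumption | Peak 10 | Peaks 14 and 18 |
|---|---|---|
| Test result does not affect later vaccination | 49.8–50.0% | 49.8–50.0% |
| Cases half as likely to be vaccinated later | 51.5–52.6% | 50.0–50.8% |
| No case ever vaccinated later | at most 54.8% | at most 51.7% |

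If only doses within 7 days of onset are visible, the last assumption gives at most 51.4%.

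**6. Over a season, not adjusted for onset week.** In a model of the same kind, with one choice of spreads, unadjusted VE was:

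| Epidemic peak (weeks) | Written rule | Status at onset | Difference (points) |
|---|---|---|---|
| 10 | 49.0% | 46.2% | 2.8 |
| 14 | 38.7% | 30.7% | 8.0 |
| 18 | 37.1% | 28.3% | 8.8 |

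With spreads of 2 to 4 weeks the difference ranged from −0.4 to 11 points. The shortfall from 50% is calendar-time confounding: cases cluster late, when coverage is high, while controls are spread over the season. Dropping early unvaccinated controls happens to offset part of it.

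**7. Is calendar time adjusted for?** It is not in Potential confounders and effect modifiers, and Measure of effect names exposure, age, sex and the confounders of interest. Study period promises early, middle and late windows, and the secondary objectives stratify by them, but neither places calendar time in the primary adjusted model.

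**The case against.** The strongest reply is that post-onset doses will rarely be seen. Data collection has the form completed by clinicians at swabbing, and the exclusion criteria remove specimens taken 8 or more days after onset. Status frozen at the swab therefore leaves at most a 7-day window in an acutely ill patient. That stands for sites that work this way. It does not close the gap, because no section freezes status at onset or swab. The permitted sources include registries and insurers, and Study sites expressly admits institutes using routine databases, which can be read after the season.

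A second reply is that such a subject could be treated as ambiguous or as partially vaccinated, and that the Sensitivity analyses section allows other exposure definitions. Either coding still removes the subject from the primary analysis, and those sensitivity analyses are optional.

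Third, the written rule can be nearer the truth than an onset-based rule when nothing is adjusted for calendar time (step 6). That stands, and it is why the definition should not be changed alone.

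Three stronger readings are tempting, and the documents do not support them.

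- A reader might infer that only subjects aged 9 or over are affected and that all younger children are handled correctly. The first block also covers children under 9 fully vaccinated last season.
- A reader might infer that the rule materially inflates VE. The documents give no loss fractions and do not fix the direction.
- A reader might take the 3 to 9 point difference in step 6 as harm done by the written rule. It is mostly calendar-time confounding, which the written rule partly masks.

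**Conclusion.** The defect in the wording is certain: in the first block a subject vaccinated only after onset has no category, and the comparator is selected on an event after the outcome. Its numerical effect is not certain. It is nil within an onset week if cases and controls are lost equally, probably small where status is frozen at swabbing, and probably a few points of VE or less over a season where records are read later, in either direction. These sizes rest on assumed loss fractions, campaign timing and epidemic timing, none of which the documents give. The point is worth acting on because the affected group is the shared comparator for every brand estimate and the repair uses data already required.

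**What to change.** Make two changes together.

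1. In Definition of vaccination status, use one rule for both blocks: *unvaccinated if there is no record of influenza vaccination before ILI/SARI symptom onset in the current season; doses dated after onset are ignored.*
2. Add onset week (calendar time) to the minimum covariate set in Potential confounders and effect modifiers, and to the adjusted model in Measure of effect.

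The first change removes selection on later events. The second prevents the restored early-season subjects from exposing the unadjusted calendar-time confounding. The cost is a sentence or two of wording and a few extra model terms. Onset date and vaccination date are already obligatory in Annex 1, so no new data are needed.

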# **Dissemination of results**

The study site will remain the owner of the data and may disseminate the study results according to their local practices. The data will also be submitted to WP7 for European pooled and/or metaanalyses. EFPIA members do not have access to this data. DRIVE will disseminate the results of its analyses according to its Communications plan (DRIVE D5.4).

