# BACKGROUND

The DRIVE consortium aims to enable the collaboration of different public and private stakeholders to perform annual brand-specific influenza vaccine effectiveness (IVE) studies for various influenza vaccines on the European market. To this end, IVE studies will be conducted at various study sites across Europe. In a second step, the site-specific data will be combined to obtain overall estimates at the European level. The purpose of this document is to provide guidance for writing the Statistical Analysis Plan (SAP) of combining and presenting information on IVE from different study sites. This document will be updated following the learnings from the pilot year 2017-2018.

There are two statistical approaches for pooling data: a one-stage or a two-stage pooling approach (1). The two-stage approach refers to the classical meta-analytical approach, also called aggregated data meta-analysis (AD-MA). In this approach, the patient-level or minimally aggregated data from each study are analysed separately in order to obtain the effect estimates of interest (here vaccine effectiveness estimates) and the corresponding confidence intervals (CIs). Then, in the second step, the effect estimates are combined by an appropriate meta-analysis model to obtain the meta-analytical (weighted averaged) estimate. The one-stage pooling approach analyses all the combined patient-level or minimally aggregated data from the different data sources in a single step. This approach is also called the individual participant data meta-analysis (IPD-MA).

We opt to pool data using the AD-MA approach, given the statistical equivalence of AD-MA and IPD-MA, given that many of the mentioned advantages of IPD-MA (i.e. transforming data to common sources or measures and standardizing analysis) can also be achieved through harmonization/standardization of the individual site-specific studies and given the additional complexity of performing IPD-MA when data are collected using different study designs (1). Within AD-MA, we prefer the use of random effects meta-analysis model, which assumes that the observed effect estimates can vary across study sites because of differences in the treatment effect in each study site (e.g. due to differences in population, in health care utilization, in circulating influenza strains) as well as sampling variability.

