### Effect measures

The effect measures for pooling are the study site-specific IVE estimates and their 95% confidence intervals (CIs).

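### Annex 1 cannot identify the potentially vaccinated group, so WP7 can neither apply nor verify its exclusion, nor run the sensitivity analysis, from the pooled dataset

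*Combined protocol and SAP*

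**What the plan says.** The protocol section Vaccination status ascertainment lists record-based sources (register, vaccination card, GP, pharmacist, insurer). It adds that interviewing the patient or relatives alone "is not a preferred method of vaccine status ascertainment but may be performed". Its coding rule follows: "When positive vaccination status is indicated only by recall or is otherwise ambiguous, the vaccination status will be coded as" *potentially vaccinated*. Definition of vaccination status lists this as a fourth class beside vaccinated, partially vaccinated and unvaccinated. It states that the partially and potentially "vaccinated groups will be excluded from primary analysis; their significance will be assessed in sensitivity analyses".

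Annex 1 carries the title "Minimum dataset for pooled data analysis (case-control studies) v4 16 Oct 2018". Its variable for current-season vaccination, seasvaccany, is obligatory and takes three values: 0 (no), 1 (yes) and 9999 (no information). The other current-season fields are brand, date and, for children under 9, the first and second dose with their brands and dates. None of these rows offers a potentially vaccinated value or records where an individual patient's status came from. No rule says which of the three values such a patient should receive.

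On pooling, Dissemination of results says: "The data will also be submitted to WP7 for European pooled and/or metaanalyses". The SAP (Annex 4, Background) says "We opt to pool data using the AD-MA approach", which is the two-stage route, and Effect measures names site-specific estimates as the quantities pooled. The protocol's Statistical analysis section still mentions one-stage pooling as a possibility. The SAP's Sensitivity analysis section commits to the protocol's sensitivity analyses.

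**The concern.** The exposure rule and the codebook do not fit together. The rule needs a class that the codebook cannot carry. The class will occur, because interview is a permitted source and the form is completed by clinicians at the time of swabbing.

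The companion group is better served. For a one-dose schedule, partially vaccinated can be derived from vaccination date and symptom onset date, both obligatory in Annex 1. Potentially vaccinated cannot be derived from any Annex 1 variable.

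Three things are at stake. First, WP7 cannot tell from the data whether a site has applied the exclusion, although the SAP's Inclusion criteria keep estimates that depart from the study protocols out of the primary meta-analysis. Second, WP7 cannot itself run the promised sensitivity analysis on this group. Third, if sites choose different codes, their estimates can differ for reasons unrelated to the vaccine, and that difference would enter the heterogeneity statistic.

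**Working it through.** The plan gives no figure on this point, so there is none to reproduce. The check has two parts.

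**What each available code does to a recall-only patient**

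- *Code 1.* The patient reports vaccination. With a date more than 14 days before onset, the record looks the same as a confirmed vaccinee. Without a date, the Missing data rule removes the patient. Without a brand, the patient cannot enter a brand-specific estimate.
- *Code 0.* The definition of unvaccinated turns on having no vaccine record for the season, which is literally true of a recall-only patient. The patient then joins the reference group.
- *Code 9999.* Read with the Missing data rule, which drops subjects with missing exposure, the patient leaves the primary analysis as intended. The patient can then no longer be told apart from someone with no information at all.

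**Effect on VE (illustration; every input is an assumption)**

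True VE is 50%, so OR = 0.5. Coverage among controls is c = 20% or 50%. Coverage among cases is p, with p/(1−p) = 0.5 × c/(1−c), so p = 0.1111 or 0.3333. A share s = 10-30% of true vaccinees is known by recall only. A share f = 2-10% of unvaccinated subjects wrongly recalls vaccination. Both shares are the same in cases and controls. A recalled date is assumed present.

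*Code 1.* True vaccinees are classed correctly whatever s is, so only f matters:

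VE = 1 − {[p + (1−p)f] / [(1−p)(1−f)]} ÷ {[c + (1−c)f] / [(1−c)(1−f)]}

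For c = 20%, f = 10%: cases 0.2000/0.8000 = 0.2500; controls 0.2800/0.7200 = 0.3889; ratio 0.643; VE = 35.7%.

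*Code 0.* False recallers are classed correctly, so only s matters:

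VE = 1 − {p(1−s) / [(1−p) + ps]} ÷ {c(1−s) / [(1−c) + cs]}

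For c = 50%, s = 30%: cases 0.2333/0.7667 = 0.3043; controls 0.3500/0.6500 = 0.5385; ratio 0.565; VE = 43.5%.

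*Code 9999.* The factors (1−s) and (1−f) cancel between cases and controls, so the OR stays at 0.5 and VE at 50%.

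| Code given to recall-only subjects | Coverage 20% | Coverage 50% |
|---|---|---|
| 1, f = 2% / 5% / 10% | 46.3% / 41.7% / 35.7% | 49.0% / 47.6% / 45.5% |
| 0, s = 10% / 30% | 49.4% / 48.2% | 47.6% / 43.5% |
| 9999 | 50.0% | 50.0% |

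Two sites with the same true VE of 50% and 20% coverage, one using code 1 and the other 9999, would differ by 50.0 − 35.7 = 14.3 points at f = 10% and by 50.0 − 46.3 = 3.7 points at f = 2%.

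**The case against.** A reader might infer that the exclusion and its sensitivity analysis cannot be run at all, and that the pooled estimate necessarily mixes confirmed with recalled vaccination. The documents do not support that. The SAP pools site-specific estimates obtained under the site protocols, and the protocol's statistical section is written for the site level. The ascertainment rule already obliges sites to make the classification. A site that keeps this information can apply the exclusion, run the sensitivity analysis and submit both results. Annex 1 is a minimum dataset, Data management allows a site its own codebook, and each site must describe how it ascertains vaccination. Code 9999 also achieves the primary exclusion without bias under the assumptions above, so mixing occurs only if code 1 is used.

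A reader might also size the problem by a site where all status is recalled and coded 1. With recall sensitivity 95% and specificity 95%, 90% and 85%, that gives VE of 40.9%, 34.7% and 30.1% at 20% coverage. These figures follow from their assumptions but describe an extreme: the protocol prefers record sources, and recalled patients without a date or brand are lost to some or all of the estimates.

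All of this stands as a limit on the consequence. It does not remove the gap. A site's own codebook is called for only when it does not follow the DRIVE one, so a site that complies has nowhere to put the class. A site-level description of sources cannot identify individual patients. Nothing in the documents tells sites to use 9999.

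**Conclusion.** The point holds as a conflict between the exposure rule and the codebook. From Annex 1 data WP7 cannot identify the potentially vaccinated group, so it can neither apply nor check the exclusion, nor run the sensitivity analysis. Under the two-stage plan both rest on consistent work at each site, without a shared code. Some Annex 1 rows are damaged in the copy reviewed. The current-season vaccination rows read without a break, so an overlooked source field is unlikely but cannot be fully excluded.

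The possible bias is conditional and moderate. Under the stated assumptions the loss is about 4 to 14 points of VE with code 1 at 20% coverage, 1 to 4.5 points with code 1 at 50% coverage, 0.6 to 6.5 points with code 0 across both coverages, and none with 9999. The documents give no recall shares or error rates, so these figures show direction and order of size only. The change should be made, but the primary analysis does not fail without it.

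**What to change.** In Annex 1, either add an obligatory fourth value to seasvaccany (2 = potentially vaccinated: recall only or ambiguous), or add an obligatory patient-level field for the source of vaccination status. If the source field is chosen, it needs categories for recall only and for otherwise ambiguous, since the protocol's class covers both. State the mapping rule beside it: only record-confirmed 1s can count as vaccinated in the primary analysis, and code 2 enters only the sensitivity analysis named under Definition of vaccination status.

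The cost is one codebook item, filled from a classification that sites must already make. Sites that rely heavily on recall will contribute fewer vaccinated subjects to the primary analysis, and a site relying on recall alone would contribute none. The protocol's exclusion already implies this; the new item makes it visible.
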